### **17.11 Publication/ Data Sharing**

Neither the complete nor any part of the results of the study carried out under this protocol, nor any of the information provided by City of Hope for the purposes of performing the study, will be published or passed on to any third party without the written approval of the Study PI. Any investigator involved with this study is obligated to provide City of Hope with complete test results and all data derived from the study.

The preparation and submittal for publication of manuscripts containing the study results shall be in accordance with a process determined by mutual written agreement between City of Hope and AstraZeneca, and participating non-COH institutions. The publication or presentation of any study results shall comply with all applicable privacy laws, including, but not limited to, the Health Insurance Portability and Accountability Act of 1996.

In accordance with the [U.S. Public Law 110-85](#) (Food and Drug Administration Amendments Act of 2007 or FDAAA), Title VIII, Section 801, this trial will be registered onto [ClinicalTrials.gov](#). Results will be reported on [ClinicalTrials.gov](#) generally within 12 months after the completion date unless criteria to delay submission are met per the final rule.

## APPENDIX A: PERFORMANCE STATUS SCALES

Karnofsky Scale %	Karnofsky Description	ECOG* Scale	ECOG Description
100	Normal, no complaints, no evidence of disease.	0	Fully active, able to carry on all pre-disease activities without restriction.
90	Able to carry on normal activity, minor symptoms or signs of disease.		
80	Normal activity with effort, some signs or symptoms of disease.		
70	Cares for self, unable to carry on normal activity or to do active work.	1	Restricted in physically strenuous activity but ambulatory and able to carry out work of a light or sedentary nature e.g. light house work office work.
60	Requires occasional assistance, but is able to care for most of own needs.	2	Ambulatory and capable of all self-care but unable to carry out any work activities. Up and about more than 50% of waking hours
50	Requires considerable assistance and frequent medical care.		
40	Disabled, requires special care and assistance.		
30	Severely disabled, hospitalization is indicated although death is not imminent.	3	Capable of only limited self-care, confined to bed or chair more than 50% of waking hours
20	Hospitalization necessary, very sick, active supportive treatment necessary.	4	Completely disabled. Cannot carry on any self-care. Totally confined to bed or chair
10	Moribund, fatal processes		
Dead		5	Dead

\*also known as Zubrod, SWOG or WHO scale

**APPENDIX B: AIHA RESPONSE CRITERIA**

Treatment response will be determined per the investigators' assessment, according to Barcellini et al.

AIHA Complete Response (CRAIHA):	Hemoglobin >12 g/dL, AND no transfusion requirements. No laboratory evidence of ongoing hemolysis (haptoglobin, indirect bilirubin WNL, reticulocyte count <1.5 ULN)
AIHA Partial Response (PRAIHA):	Hemoglobin level ≥10 g/dL (without transfusions), OR hemoglobin increase of at least 2 g/dL above pretreatment level, Presence of laboratory evidence of ongoing hemolysis.

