
Autoimmune hemolytic anemia (AIHA) is a life-threatening disease with an incidence of 1-3 per 100,000 persons per year. In addition to idiopathic AIHA, a number of underlying conditions have been associated with this disorder, including viral infections, autoimmune and connective tissues diseases, and lymphoproliferative disorders. AIHA is particularly common among patients with chronic lymphocytic leukemia (CLL) with an incidence of ~2.3% as reported in a recent retrospective analysis of 1750 patients. First-line therapy of AIHA typically consists of corticosteroids, which induce initial responses in 70%-85% of patients with warm AIHA; however, only one-third of patients remain in long-term remission after stopping corticosteroids, and a further 50% require maintenance doses. Subsequent lines of immunosuppressive therapy carry initial response rates from 40-60%, though relapses are similarly common. Therefore, in the relapsed/refractory setting, safe and effective treatments for AIHA are needed. Ibrutinib, a small molecule inhibitor of Bruton tyrosine kinase (BTK), inhibits B-cell activity and has been shown to inhibit production of auto-antibodies in murine models of autoimmunity, suggesting their potential efficacy in multiple autoimmune conditions. Preliminary evidence suggests that ibrutinib may be efficacious in treatment of CLL-associated AIHA, as 50% of patients who presented with hemolysis and received therapy with the BTK inhibitor were able to discontinue immunosuppressive therapy. A second-generation selective BTK inhibitor, acalabrutinib, may be associated with fewer off-target effects including diminished frequency of side effects including bleeding and atrial fibrillation, and showed increased efficacy against AIHA in a murine model. This study will assess if acalabrutinib can increase hemoglobin and reduce transfusion requirements in patients with relapsed or refractory AIHA.
	
Treatment Description	

Eligible participants enrolled in this study will receive acalabrutinib (100 mg, PO BID) for 12 cycles. Participants that experience disease progression or unacceptable toxicities will discontinue study drug and be removed from study. Treatment with acalabrutinib may be continued beyond 12 cycles, for a maximum of 36 cycles, if the study participant might benefit from ongoing therapy in the opinion of treating physician (e.g., ongoing therapy for CLL is required).
	
Objectives	

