### **5.10.6 Transfusions of platelets and red blood cells**

Platelet transfusions are permitted as medically necessary per institutional guidelines (e.g., for platelets <10,000/µL in the absence of clinical bleeding). Each transfusion event (and number of units given) will be recorded in the CRF.

Red blood cell transfusion should be considered for all participants with anemia, especially those with hemoglobin values ≤6 g/dL. Each transfusion event (and number of units given) will be recorded in the CRF.

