
a. Ideally the clinic visit and all the study requirements should be performed on Day 1 of each cycle as indicated, but may be performed within 7 days before or after the scheduled day. Each treatment cycle is 28 days
 
b. Screening activities to occur within 30 days prior to the start of protocol therapy.
 
c. Protocol therapy may last up to 12 cycles, until unacceptable toxicity or disease progression (see Section 5.6 for more comprehensive list). At the end of 12 cycles, treatment with acalabrutinib may be continued if the study participant might benefit from the ongoing therapy in the opinion of the treating physician.
 
d. An End of Treatment (EOT) visit is required for safety assessments for any subjects who permanently discontinue study drug for any reason, including disease progression. This visit should occur at 30 (<math>\pm 7</math>) days from time of the last dose of study drug to monitor for resolution or progression of AEs and to document the occurrence of any new events, regardless of whether the subject receives a new CLL therapy or demonstrates disease progression within this timeframe. Subjects who withdraw consent for study treatment should still be encouraged to complete the EOT assessments, but these assessments cannot be mandated if subject consent for further study participation is withdrawn.
 
e. Follow-up assessments are to occur in accordance with standard of care, with participants visits occurring at least every 4 months, up to 12 months from time last dose of study drug.
 
f. Informed consent process to be fully documented (see Section 17.4). Informed consent must occur prior to any research only (non-SOC) screening procedures.
 
g. A medical history will be obtained by the investigator or qualified designee. To include information on demographics, all active conditions, and any condition diagnosed within the prior 10 years that are considered to be clinically significant by the Investigator. Details regarding the participant's cancer will be recorded separately and not listed as medical history.
 
h. Eligibility criteria are detailed in Section 3.0.
 
i. Registration into a COH clinical trial management system (CTMS)
 
j. Document the following disease-specific information: number of prior treatment regimens for CLL and AIHA; drugs previously used in the therapy of CLL and AIHA; including (if available): therapy dates, and response, concomitant autoimmune disorders, including hematologic (immune thrombocytopenia, immune-mediated neutropenia) and non-hematologic (e.g., rheumatoid arthritis and other rheumatologic conditions; inflammatory bowel disease [Crohn's disease, ulcerative colitis]), History of ibrutinib intolerance (present versus not), Rai stage at diagnosis (if known) and the time of study entry.
 
k. Current list of medications will be acquired concurrent with medical history. See Section 5.9 for concomitant medication restrictions and guidelines. Baseline transfusion requirements must be assessed prior to start of study drug. Transfusion requirements prior to study start up to 6 months will be collected/documents, if available. Transfusion requirement will be assessed on day 1 of each cycle and number of units of PRBCs and platelets transfused during the previous cycle will be documented. Enter new medications started during the trial through the end of treatment visit. Record all medications taken for grade 3 and 4 SAEs.
 
l. Physical examination must be performed by a medically qualified individual such as a licensed physician, Physician's Assistant or advanced Registered Nurse Practitioner as local law permits. Baseline complete physical exam per institutional standards and may include evaluating: weight, general appearance, head, ears, eyes, nose, throat, neck, skin, cardiovascular system, respiratory system, gastrointestinal system, and nervous system. Height is only required as part of screening. Weight should be recorded at each visit. More extensive physical exams will be performed if guided by the development of new symptoms.
 
m. Vital signs: blood pressure, heart rate, temperature, and oxygen saturation by pulse oximetry.
														

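### The 2 g/dL partial-response limb in Appendix B has no transfusion condition, so a transfused hemoglobin rise can count toward the primary endpoint

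*Combined protocol and SAP*

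**What the plan says.** Section 11.1 defines the primary endpoint as the proportion of patients in AIHA complete or partial response after 6 cycles and refers to Appendix B for the criteria. Appendix B states that "Treatment response will be determined per the investigators' assessment", according to a cited publication, and then prints its own definitions:

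- Complete response: hemoglobin above 12 g/dL with "no transfusion requirements" and no laboratory evidence of ongoing hemolysis.
- Partial response, first limb: "Hemoglobin level ≥10 g/dL (without transfusions").
- Partial response, second limb, joined by OR: "hemoglobin increase of at least 2 g/dL above pretreatment level".

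On transfusion, Section 5.10.6 says that "Red blood cell transfusion should be considered for all participants with anemia", with emphasis on values of 6 g/dL or below, and has each event and the units recorded. Section 10.0, footnote k, adds that the "number of units of PRBCs and platelets transfused during the previous cycle will be documented". Transfusion-dependent patients are eligible (Synopsis; Section 3.1, item 4).

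On steroids, Section 3.2, item 10, allows rescue use during the trial. Section 5.10.1 permits concomitant steroids for AIHA, with a taper to 20 mg/day or less of prednisone equivalent anticipated by 8 weeks. Neither section ties steroid use to response scoring.

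Section 12.2 sets the decision rule: one-sided exact binomial test, 20 evaluable patients, null rate 30%, alternative 60%, rejection at 10 or more responders.

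**The concern.** The Synopsis says the study will "assess if acalabrutinib can increase hemoglobin and reduce transfusion requirements". A hemoglobin rise produced by transfused cells is not evidence of that, and the definitions of complete response and of the first PR limb both guard against it. The second PR limb does not. A patient who goes from 6 to 8 g/dL after transfusion meets its words.

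This matters because PR counts fully toward the primary endpoint, there is no control arm in which the same scoring would occur, and the conclusion depends on one count. With 9 true responders, one transfused patient scored PR turns a negative result into a positive one. The secondary endpoint on transfusion frequency (Sections 11.2 and 12.4.2) would show that such patients exist, but nothing links it to how response is scored.

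A lesser point of the same kind concerns rescue steroids. A rescued patient who stays on acalabrutinib through 6 cycles is scored on hemoglobin and hemolysis alone, whether or not the steroid produced the rise.

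**Working it through.** **Step 1. Which patients depend on the second limb.** A patient who meets the second PR limb but not the first is in one of two groups:

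- Final hemoglobin is below 10 g/dL. With a rise of at least 2 g/dL, the starting value was below 10 − 2 = 8 g/dL. If untransfused, this is a real improvement that the limb presumably exists to capture.
- The patient was transfused. The first limb then excludes the patient, and the second takes the patient back in if the rise is at least 2 g/dL, whatever the starting value.

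The second group is the gap. A search of Sections 5.10.6, 10.0, 11.1, 11.2, 12.4.1 and 12.5 finds no text that excludes it.

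**Step 2. Reproduce the plan's figures (Section 12.2).** With X the number of responders in 20 and rejection at X ≥ 10:

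- P(X ≥ 10 | p = 0.30) = 0.0480. The plan states 0.048.
- P(X ≥ 10 | p = 0.60) = 0.8725. The plan states about 87%.

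Both agree.

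**Step 3. Illustrate the effect of mis-scoring.** Let r be the share of true non-responders scored PR only because of a transfused rise. The documents give no value, so r is assumed. At a true rate of 30% the apparent rate is p = 0.30 + 0.70r, and the expected number mis-scored is 20 × 0.70 × r.

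| r (assumed) | Expected mis-scored of 20 | Apparent rate | P(X ≥ 10) |
|---|---|---|---|
| 0 | 0 | 0.300 | 0.048 |
| 2% | 0.28 | 0.314 | 0.064 |
| 5% | 0.70 | 0.335 | 0.095 |
| 10% | 1.40 | 0.370 | 0.165 |

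This takes 30% as a rate that excludes such patients.

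**Step 4. Cost of closing the gap.** Let s be the share of true responders lost because they were transfused for another reason inside the look-back (assumed). At the alternative, p = 0.60 × (1 − s):

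| s (assumed) | p | Power |
|---|---|---|
| 0 | 0.600 | 0.872 |
| 2% | 0.588 | 0.848 |
| 5% | 0.570 | 0.805 |

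**Step 5. Rescue steroids.** Section 11.1 makes evaluable anyone with at least 6 cycles and an AIHA evaluation, and Appendix B scores them without mentioning steroids. Three provisions narrow the route: AIHA relapse ends protocol therapy (Section 5.6), stopping before 6 cycles for AIHA progression counts as non-response (Section 11.1), and the steroid taper is anticipated by week 8 (Section 5.10.1). Six cycles last 6 × 28 = 168 days, or 24 weeks, so the anticipated taper ends 24 − 8 = 16 weeks before the assessment. What remains is mainly a patient rescued shortly before it, or one rescued without being judged to have relapsed or progressed.

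**The case against.** **The cited publication may supply the condition, and investigators judge response.** Both are possible. The publication was not available for this review, so nothing is claimed about its content. But Appendix B prints its own criteria, with the qualifier on one PR limb and not on the other. In an open-label trial with investigator-assessed response, sites should not have to infer the missing words.

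**Frequency is unknown and the shares are assumed.** This stands. At the 2% share the increase is 0.064 − 0.048 = 0.016. If the 30% benchmark already includes transfused rises, the increase is smaller or nil.

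**The transfusion text is aimed mainly at very low values.** In part. Section 5.10.6 stresses values of 6 g/dL or below, but its recommendation covers all participants with anemia.

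**On steroids, a reader might infer that the plan does not say how a rescued patient who stays on acalabrutinib is scored.** The documents do not support that. Section 11.1 with Appendix B does score such a patient, on hemoglobin and hemolysis. What is absent is a steroid condition, which is a design choice and not a missing rule. Early rescue also need not mean that the drug had no effect. Section 2.1.3 reports a median of 4.7 months on ibrutinib before therapy for autoimmune cytopenia was stopped.

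**Conclusion.** The transfusion gap is real on the protocol's own wording and should be closed before the primary analysis. As written, a transfused rise of 2 g/dL or more can count as PR, contrary to the stated aim and to the conditions on complete response and the first PR limb. For assumed mis-scoring of 2% to 10% of true non-responders, the chance of a false positive conclusion is 0.064 to 0.165 instead of 0.048. This rests on the assumed shares and on a 30% null that excludes such patients.

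A reader might go further and infer that the stated type I error is wrong or that the trial will overstate response. The documents do not support either. The design figures reproduce exactly, and whether any patient would be scored this way is not known.

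The steroid point is secondary. It warrants a sensitivity analysis, not a change to the primary rule.

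**What to change.** 1. In Appendix B, apply the no-transfusion condition to both PR limbs, over a look-back before the response assessment that the sponsor states in advance. Derive it from the transfusion records already collected under Section 5.10.6 and Section 10.0, footnote k.
2. In Section 12.4.1, add a sensitivity analysis of the primary endpoint that counts as non-responders those given rescue steroids for AIHA within a pre-stated window before the post-cycle-6 assessment. Define rescue so that it is distinct from the concomitant steroids that Section 5.10.1 permits. The sources are the concomitant-medication records (Section 5.9.1; Section 10.0, footnote k; Table 13.3). Section 5.9.1 names only the agent and the reason, so confirm that the form dates steroid use well enough to apply the window.

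The cost is one wording change, one derivation rule and one extra analysis. The downside is that a true responder transfused for another reason inside the look-back would no longer count. If that removes 2% or 5% of true responders (assumed), power falls from 0.872 to 0.848 or 0.805. These changes concern scoring and analysis only; no dose or clinical rule is proposed.

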## 11.0 ENDPOINT DEFINITIONS/MEASUREMENT OF EFFECT

### 11.1 Primary Endpoint(s)

Objective	Endpoint	Start	End
Assess the efficacy of acalabrutinib in CLL patients with relapsed or refractory AIHA	AIHA ORR after 6 cycles [ORR defined as proportion of patients who achieve complete and partial response; refer to Appendix B ]	First dose of study drug [i.e. C1 Day 1]	After 6 cycles of therapy

Primary endpoint of AIHA ORR after 6 cycles will be defined as the proportion of patients achieving AIHA complete or partial response after 6 cycles. Patients evaluable for this endpoint include: 1) those who receive at least 6 cycles of treatment and have AIHA response evaluation after 6 cycles (each cycle = 28 days); 2) patients who terminate acalabrutinib prior to completing 6 cycles due to AIHA or CLL progressive disease (they will be counted as non-responders).

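### On its most natural reading, Appendix B leaves a patient with resolved hemolysis and hemoglobin of 10 to 12 g/dL outside both CR and PR, so that patient counts against the drug in the primary analysis

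*Combined protocol and SAP*

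**What the plan says.** Appendix B defines two AIHA response categories and no others.

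- **CR:** "Hemoglobin >12 g/dL", no transfusion requirement, and "No laboratory evidence of ongoing hemolysis (haptoglobin, indirect bilirubin WNL, reticulocyte count <1.5 ULN").
- **PR:** "Hemoglobin level ≥10 g/dL (without transfusions"), or, as the second limb, "hemoglobin increase of at least 2 g/dL above pretreatment level, Presence of laboratory evidence of ongoing hemolysis".

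Appendix B assigns the scoring to the sites: "Treatment response will be determined per the investigators' assessment", following a cited publication.

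Section 11.1 builds the primary endpoint on these categories alone: "ORR defined as proportion of patients who achieve complete and partial response; refer to Appendix B". The first group in its denominator is "those who receive at least 6 cycles of treatment and have AIHA response evaluation after 6 cycles". Sections 11.1.1 and 11.2.1 refer back to Appendix B. No section gives a category or a tie-break for a patient who meets neither definition.

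Section 12.2 sets the test: one-sided exact binomial, 20 evaluable patients, null 30%, target 60%, rejection at 10 or more responders, power about 87%, actual type I error 0.048.

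**The concern.** CR asks that hemolysis be absent and PR lists it as present. The two hemoglobin ranges do not meet once hemolysis has stopped, because CR starts above 12 g/dL while PR, which starts at 10 g/dL, is closed to that patient. The ordering is then perverse: of two patients with the same hemoglobin, the one whose hemolysis has resolved scores worse.

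Such patients are plausible in this population. Section 6.1 lists anemia among the very common reactions to acalabrutinib, and Appendix C accepts 11 g/dL as enough hemoglobin for a CLL complete remission. Hemoglobin may therefore stay at or below 12 g/dL for reasons other than hemolysis. This shows that the case can arise, not how often.

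At stake are the primary response rate and the endpoints that use the same criteria: AIHA ORR after 3 and 12 cycles, and the starting point of AIHA sustained response. The trial is open-label with investigator-assessed response, so an unclear row can also be read differently from site to site.

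**Working it through.** **1. Classification.** Take four untransfused patients, each starting at 7.5 g/dL (illustrative values). The PR row can be read in three ways: (A) ongoing hemolysis is required for both limbs; (B) it is required only for the 2 g/dL limb; (C) it is allowed but not required.

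| Hemoglobin after 6 cycles | Hemolysis | CR? | PR under A | PR under B | PR under C |
|---|---|---|---|---|---|
| 11.6 | ongoing | no | yes | yes | yes |
| 11.6 | resolved | no (not above 12) | **no** | yes | yes |
| 9.5 (7.5 + 2) | ongoing | no | yes | yes | yes |
| 9.5 (7.5 + 2) | resolved | no | **no** | **no** | yes |

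Reading A is the most natural. The CR row also adds its hemolysis condition without a connector, and there it is plainly required. Under A, both resolved patients are unclassified. Section 11.1 keeps them in the denominator and counts only CR and PR in the numerator, so they are non-responders.

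**2. The plan's own figures.** With X ~ Bin(20, p) and rejection at X ≥ 10:

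- P(X ≥ 10 | 0.30) = 0.048, as stated.
- P(X ≥ 10 | 0.60) = 0.872, matching the stated 87%.

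**3. One patient.** P(X ≥ 9 | 0.30) = 0.113 and P(X ≥ 10 | 0.30) = 0.048. Moving one gap patient from non-responder to responder takes the result from not rejecting to rejecting.

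**4. Power, under an assumption.** Suppose that the planned 60% was meant to include gap patients, and that a fraction f of all patients falls in the gap. The scored rate is then 0.60 − f, and power is P(X ≥ 10 | 0.60 − f). The documents do not give f.

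| f (assumed) | Expected gap patients of 20 | Share of the 60% (f / 0.60) | Scored rate | Power |
|---|---|---|---|---|
| 0 | 0 | 0% | 0.60 | 0.872 |
| 5% | 1 | 8% | 0.55 | 0.751 |
| 10% | 2 | 17% | 0.50 | 0.588 |
| 15% | 3 | 25% | 0.45 | 0.409 |

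If the 60% was set for the strict definition, the first row applies whatever f is.

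**5. The other side of widening PR.** If the no-benefit rate under a wider definition were above 30%, the type I error at 10 of 20 would rise: P(X ≥ 10 | 0.33) = 0.087 and P(X ≥ 10 | 0.35) = 0.122. Both rates are assumptions.

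**The case against.** The best reply is that the text is ambiguous rather than wrong. CR uses an explicit AND and PR an explicit OR, but nothing joins the hemolysis clause to the rest of the PR row, and table layout may have been lost in reading the PDF. An investigator could take the clause as descriptive and score the patient a PR, and the cited publication may settle the point. This stands in part. A reader might infer that the protocol states outright that these patients are non-responders. It does not: that follows from reading A together with Section 11.1. But a primary endpoint that turns on which reading a site adopts still needs repair, and nothing in the documents chooses between them. The cited publication was not available, so nothing here rests on it.

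Second, the gap may be narrower than it looks. The PR row names no markers, and the Section 10.0 footnote on hemolysis parameters includes LDH and DAT, which the CR row does not list. An investigator who counts a raised LDH or a positive DAT as ongoing hemolysis would score PR. This stands, and it is a further source of inconsistent scoring.

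Third, a reader might take the marrow-involvement wording in inclusion criteria 8 and 9 as showing that low hemoglobin without hemolysis is expected. Those criteria concern neutrophils and platelets and do not support that.

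Fourth, a reader might conclude that the trial is underpowered. The documents do not show this. Section 12.2 does not say which definition the 60% refers to, and the affected fraction is unknown.

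**Conclusion.** The point holds as a defect in the primary-endpoint definition. On the most natural reading, resolved hemolysis at 10 to 12 g/dL (12.0 included), or after a rise of at least 2 g/dL to below 10, is neither CR nor PR and counts as non-response, while the same hemoglobin with continuing hemolysis is a PR. Another reading is possible, so scoring may also differ between investigators.

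That one patient can change the conclusion at 9 versus 10 of 20 is exact and needs no assumption about frequency. The fall in power from 0.872 to 0.751, 0.588 or 0.409 needs two assumptions: that the 60% was meant to include these patients, and that 5%, 10% or 15% of all patients are affected. The sample-size calculation itself reproduces and is not in dispute.

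**What to change.** Before the primary analysis, and preferably before six-cycle responses are reviewed:

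1. Reword the PR row so that a patient who does not meet CR, and who meets either hemoglobin limb without transfusion support, is a PR whether or not laboratory hemolysis persists. Do not simply append a phrase making hemolysis optional. The no-transfusion condition now sits only on the 10 g/dL limb, so that shortcut would newly credit a transfused rise of 2 g/dL with no hemolysis, which the current text on reading A does not.
2. State which markers count as laboratory evidence of hemolysis, so that the CR row and the sensitivity analysis are applied alike at all sites.
3. Confirm in Section 12.2 that the 30% null and the 60% target refer to the reworded definition.
4. Report ORR under the strict reading as a sensitivity analysis.

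The cost is a short amendment to Appendix B and a sentence or two in Section 12. No new data are needed, since hemoglobin, transfusions and hemolysis markers are already collected. The downside is a slightly wider PR: if the no-benefit rate under it exceeded 30%, the type I error would exceed 0.048 (0.087 at an assumed 33%). Step 3 addresses this.

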##### Nature of Illness and Illness Related Criteria

\_\_\_4. "Warm" or "cold" AIHA in patients with CLL, relapsed/refractory (RR) after first line treatment with oral prednisone (with or without rituximab), defined as:

- anemia ( $Hgb \leq 10$  g/dL; or  $Hgb > 10$  g/dL dependent on transfusions or maintenance therapy (rituximab, cyclosporin, etc) to maintain this level of hemoglobin, and
- laboratory evidence of hemolysis – presence of 3 of 4 markers (increased reticulocyte count, increased indirect bilirubin, increased lactate dehydrogenase, absent haptoglobin)

\_\_\_5. Positive DAT (score  $\geq 1+$ ) – either IgG DAT, C3 DAT, or both. Eligibility of patients with Coombs-negative AIHA should be confirmed by the trial investigator at each respective study site.

\_\_\_6. Histologically or flow cytometry confirmed diagnosis of CLL/SLL

\_\_\_7. Participant must be able to swallow tablets or capsules.

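### The +2 g/dL limb of partial response is not protected from transfusion at either end, so patients can be mis-scored in the primary endpoint, with a net bias of unknown sign

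*Combined protocol and SAP*

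**What the plan says.** The primary endpoint (section 11.1) is the "proportion of patients achieving AIHA complete or partial response after 6 cycles". Appendix B gives PR two alternative hemoglobin limbs, joined by OR. The first is "Hemoglobin level ≥10 g/dL (without transfusions", where the bracket closes. The second is a "hemoglobin increase of at least 2 g/dL above pretreatment level". The second limb carries no transfusion condition, and the appendix does not say which sample is the pretreatment one.

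The Study Calendar (section 10.0) schedules hematology at screening and again at C1D1. Footnote b adds: "Screening activities to occur within 30 days prior to the start of protocol therapy". Either sample could therefore serve as the reference.

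Inclusion criterion 4 (section 3.1) admits patients with hemoglobin above 10 g/dL who are "dependent on transfusions or maintenance therapy (rituximab, cyclosporin, etc) to maintain this level of hemoglobin", as well as those at or below 10 g/dL. Section 5.10.6 states: "Red blood cell transfusion should be considered for all participants with anemia, especially those with hemoglobin values ≤6 g/dL". Footnote k states: "Baseline transfusion requirements must be assessed prior to start of study drug". It also says that the "number of units of PRBCs and platelets transfused during the previous cycle will be documented" on day 1 of each cycle. No rule connects these records to either hemoglobin value in the +2 comparison.

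**The concern.** A change from baseline measures drug effect only if neither value has been moved by something else. Here a red-cell transfusion can move either one.

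If the reference sample follows a transfusion, the bar for the +2 limb goes up. The limb adds to the 10 g/dL limb only when the reference is below 8 g/dL, so it serves the most anemic patients, who are also those section 5.10.6 singles out for transfusion. Two patients with the same untransfused hemoglobin could then face different PR thresholds because of transfusion timing alone, and a true untransfused rise of 2 g/dL or more could be scored as non-response.

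If the cycle-6 sample follows a transfusion, the +2 limb as written can be met with little or no drug effect. In a single-arm test against a fixed 30%, that error favors a false positive conclusion. With 20 evaluable patients and a rule of 10 responders, a few such cases matter.

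**Working it through.** **1. The plan's own figures.** Section 12.2 gives 20 evaluable patients, success at 10 or more responders, a null rate of 0.30 and a target of 0.60. From exact binomial tails, P(X ≥ 10 | 20, 0.30) = 0.0480 and P(X ≥ 10 | 20, 0.60) = 0.8725. The stated 0.048 and 87% reproduce.

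**2. Effect of a transfused reference.** Let H be the untransfused level before treatment and T the lift from a recent transfusion. The documents give no value for T; 0, 1 and 2 g/dL are assumed. For an untransfused on-study reading, the PR threshold is min(10, H + T + 2), so the required true rise is min(10, H + T + 2) − H:

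| H (g/dL) | T = 0 | T = 1 | T = 2 |
|---|---|---|---|
| 5 | 2 | 3 | 4 |
| 6 | 2 | 3 | 4 |
| 7 | 2 | 3 | 3 |
| 8 | 2 | 2 | 2 |
| 9 | 1 | 1 | 1 |

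The 10 g/dL limb caps the requirement at 3 from H = 7 and removes the penalty from H = 8 upward.

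**3. Effect of a transfused on-study value.** Let U be the lift at the assessment. The +2 limb is met when the true rise is at least 2 + T − U. With U = T the requirement returns to 2. With T = 0 and U = 2 it is 0, so PR is scored with no drug effect.

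**4. Power, reference problem only.** Assumptions, none of them in the documents: a share s of evaluable patients starts at an untransfused 6 g/dL with a transfused reference; their on-drug rise is normal with mean 3 and SD 2 g/dL; their on-study value is untransfused; the correctly scored overall rate is 0.60.

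Scored rate = 0.60 − s × [P(rise ≥ 2) − P(rise ≥ 2 + T)], where P(rise ≥ 2) = 0.691, P(rise ≥ 3) = 0.500 and P(rise ≥ 4) = 0.309. The bracket is 0.191 for T = 1 and 0.383 for T = 2. Power is P(X ≥ 10 | 20, scored rate).

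| s | Rate, T = 1 | Power, T = 1 | Rate, T = 2 | Power, T = 2 |
|---|---|---|---|---|
| 5% | 0.590 | 85.3% | 0.581 | 83.2% |
| 10% | 0.581 | 83.2% | 0.562 | 78.3% |
| 15% | 0.571 | 80.8% | 0.543 | 72.9% |
| 30% | 0.543 | 72.9% | 0.485 | 53.5% |

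If the affected patients start at 7 instead of 6, the cap makes T = 2 equivalent to T = 1, and the lowest power in the table is 72.9%.

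**5. Type I error, on-study problem only.** If a share s of true non-responders is scored PR through an on-study transfusion, the apparent null rate is 0.30 + 0.70 × s. For s = 5% this is 0.335, with P(X ≥ 10) = 9.5%. For s = 10% it is 0.37, with 16.5%. These shares are also assumptions.

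**The case against.** A reader might infer that the sickest patients must rise 3 to 4 g/dL to count as responders. The documents do not support that as a general statement. It needs a transfused reference, an assumed lift of 1 to 2 g/dL, an untransfused level below 8 (6 or lower for the figure of 4) and an untransfused assessment. Any patient who reaches 10 g/dL without transfusion is a PR whatever the reference.

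A reader might also infer that the primary rate is understated. A transfused reference, taken alone, can only raise the threshold. But the same limb leaves the on-study value open, and that error runs upward. The documents give no frequency for either, so the net sign is unknown.

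The strongest case for leaving the text alone has three parts. Response is assessed by the investigator according to a cited publication, which may define the reference. Investigators may in practice apply the transfusion condition to both limbs. And transfusion records are collected, so a sensitivity analysis is possible without redefining the endpoint. The last part stands, and the fix uses it. The first two cannot be confirmed from the protocol. Appendix B writes the criteria out and places the condition on one limb only, so a site following it literally could score either way.

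It is also fair to object that correcting the reference alone could do harm. Take an untransfused level of 6 and a transfused reference of 8: the +2 limb needs 10. With the reference corrected to 6 and the assessment left open, a transfused on-study 8 would score PR. A pre-transfusion value used as the reference is likely to be a low one, and with no control arm any regression to the mean counts as response. Both objections stand and shape the fix.

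**Conclusion.** The concern holds as a defect in the response definition. The +2 g/dL limb is exposed to transfusion at both the reference and the assessment, and following Appendix B as written can misclassify patients in the primary endpoint. That the reference is undefined, and that only one limb carries the transfusion condition, rests on the text alone. So does the finding that a raised reference matters only for untransfused levels below 8 g/dL.

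The size rests on assumptions. On the reference side, power falls from 87% to between about 85% and 53.5%. The low end requires 30% of patients to start at 6 g/dL, each with a 2 g/dL lift, and is a worst case. On the assessment side, mis-scoring 5% of true non-responders roughly doubles the type I error, to 9.5%. Neither figure is a forecast, and no single corrected response rate can be computed. The stated sample size, decision rule, alpha and power are correct for the design and need no change.

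**What to change.** In Appendix B:

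- Define pretreatment hemoglobin as the last value before first dose that is free of recent red-cell transfusion, over an interval set by the sponsor, and state the fallback when no such value exists.
- Apply the same transfusion-free condition to the on-study hemoglobin for both PR limbs, and say how a patient with no qualifying on-study value is scored. Section 12.5 allows participants with insufficient data to be excluded, so silence here could move such patients out of the denominator.
- Use the same reference at 3, 6 and 12 cycles.

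In section 12.4.1, add a sensitivity analysis of the primary endpoint using the C1D1 value as the reference, based on the transfusion records collected under footnote k and section 5.10.6.

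Both ends should change together, because correcting the reference alone makes false PRs easier. The change affects scoring only, not when patients are transfused. The cost is some appendix wording and one extra baseline field (the reference hemoglobin with its date relative to the last transfusion). The downside is some regression to the mean where a pre-transfusion fallback value is used; the C1D1 sensitivity analysis would show how far the result depends on it.
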